6.3. Other Endpoints

6.3.1. PK Endpoints

Blood CCI samples for PK analysis of PF-07321332 CCI will be taken according to the Schedule of Activities given in the protocol.

The following PK parameters will be calculated for PF-07321332 (if possible) CCI [REDACTED] from the concentration-time data using standard noncompartmental methods:

Table 2. Noncompartmental PK Parameters

Key: A=analyzed using statistical model, D=displayed with descriptive statistics, ln=natural-log transformed, NA=not applicable, CCI [REDACTED] *=if data permits.

6.3.2. PD Endpoints

None.

6.4. Covariates

None.

7. HANDLING OF MISSING VALUES

For the analysis of safety endpoints, the sponsor data standard rules for imputation will be applied.

7.1. Concentrations Below the Limit of Quantification

In all data presentations (except listings), concentrations below the limit of quantification (BLQ) will be set to zero. (In listings BLQ values will be reported as “<LLQ”, where LLQ will be replaced with the value for the lower limit of quantification).

7.2. Deviations, Missing Concentrations and Anomalous Values

In summary tables and plots of median profiles, statistics will be calculated having set concentrations to missing if 1 of the following cases is true:

1. A concentration has been collected as ND (ie, not done) or NS (ie, no sample);

2. A deviation in sampling time is of sufficient concern or a concentration has been flagged anomalous by the pharmacokineticist.

Note that summary statistics will not be presented at a particular time point if more than 50% of the data are missing.

7.3. Pharmacokinetic Parameters

Actual PK sampling times will be used in the derivation of PK parameters.

If a PK parameter cannot be derived from a subject's concentration data, the parameter will be coded as NC (ie, not calculated). (Note that NC values will not be generated beyond the day that a subject discontinues).

In summary tables, statistics will be calculated by setting NC values to missing; and statistics will be presented for a particular hepatic function group with ≥ 3 evaluable measurements.

For statistical analyses (ie analysis of variance), PK parameters coded as NC will also be set to missing; and analyses will not be performed for a particular parameter if more than 50% of the data are NC.

If an individual subject has a known biased estimate of a PK parameter (due for example to an unexpected event such as vomiting before all the compound is adequately absorbed in the body), this will be footnoted in summary tables and will not be included in the calculation of summary statistics or statistical analyses.

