### **9.3. Statistical Analyses**

The SAP will be developed and finalized before any analyses are performed and will describe the analyses and procedures for accounting for missing, unused, and spurious data. This section is a summary of the planned statistical analyses of the primary and secondary endpoints.

One-way ANOVA will be used to compare the natural log transformed  $AUC_{last}$ ,  $AUC_{inf}$  (if data permit) and  $C_{max}$  for PF-07321332 between Cohort 2 with moderate hepatic impairment

(Test) and Cohort 1 with normal hepatic function (Reference). Estimates of the adjusted mean differences (Test-Reference) and corresponding 90% CIs will be obtained from the model. The adjusted mean differences and 90% CIs for the differences will be exponentiated to provide estimates of the ratio of the adjusted geometric means (Test/Reference) and 90% CIs for the ratios.

Box and whisker plots for individual participant parameters ( $AUC_{inf}$  and  $C_{max}$ ) will be constructed by cohort and overlaid with geometric means.

For summary statistics and median/mean plots by sampling time, the nominal PK sampling time will be used. For individual participant plots by time, the actual PK sampling time will be used.

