2.1. Study Design

This is a Phase 1, non-randomized, open-label study to investigate the effect of hepatic impairment on the plasma PK, safety and tolerability of a single oral dose of PF-07321332 in combination with the PK boosting agent ritonavir in approximately 16 participants. The study will be conducted in adult participants with stable, moderate hepatic impairment and a control group of participants with normal hepatic function.

Enrollment will be in a staged manner such that participants with hepatic impairment (Cohort 2) will begin enrollment first. Participants without hepatic impairment (Cohort 1) will begin recruitment towards the end of Cohort 2 or earlier, at the sponsor's discretion such that the enrollment in both cohorts may overlap. Participants in Cohort 1 will match the average demographics (at a minimum, age and weight; gender and race as much as practically possible) of participants in Cohort 2.

All participants in both cohorts will provide informed consent and undergo Screening evaluations to determine their eligibility. Categorization of participants into hepatic impairment cohort, Cohort 2, will be done based on Child-Pugh scores.

Participants who prematurely discontinue for non-safety related reasons may be replaced, at the discretion of the PI and sponsor study team.

Each enrolled participant will receive a single 100 mg dose of PF-07321332 administered orally in combination with the PK boosting agent ritonavir administered as a 100 mg dose at -12, 0, 12, and 24 hours relative to PF-07321332 dosing.

The total planned duration of participation, from the Screening visit to the last Follow-up phone call, is approximately up to 9 weeks.

Table 1. Hepatic Function Categories Based on Child-Pugh Score

Cohort	Description	Child-Pugh Score	Number of Participants
1	Without hepatic impairment	Not Applicable	8
2	Moderate hepatic impairment	Class B (7 to 9 points)	8

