- A summary of concentrations by hepatic function group and nominal time postdose, where the set of statistics will include n, mean, median, standard deviation, coefficient of variation (cv), minimum, maximum and the number of concentrations above the lower limit of quantification.
- Median concentrations time plots (on both linear and semi-log scales) against nominal time postdose by hepatic function group (all hepatic function groups on the same plot per scale, based on the summary of concentrations by hepatic function group and time postdose).

- Mean concentrations time plots (on both linear and semi-log scales) against nominal time postdose by hepatic function group (all hepatic function groups on the same plot per scale, based on the summary of concentrations by hepatic function group and time postdose).
- Individual concentration time plots by hepatic function group (on both linear and semi-log scales) against actual time postdose (there will be separate spaghetti plots for each hepatic function group per scale).
- CCI [REDACTED]
[REDACTED].

For summary statistics, median and mean plots by sampling time, the nominal PK sampling time will be used, for individual subject plots by time, the actual PK sampling time will be used.

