10. APPENDICES

Appendix 1. SAS CODE FOR ANALYSES

An example of the PROC GLM code is provided below:

```
proc mixed data = tab.pk covtest alpha=0.1;
  class group;
  model l&var = group / S covb alpha=0.1 CL DDFM=KR;
  repeated/type=un subject=subjid group=group R;
  lsmeans group;
  estimate 'Moderate vs Normal'      group 1 -1;
  ods output lsmeans = lsmeans&var;
  ods output solutionf = solution&var;
run;
```

/* Letter assignments for group within the estimate statement above are as follows;

A = *Moderate* (Test);
B = *Normal* (Reference); */;

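### Must SAP 7.3 state whether the 50% limit on uncalculated PK parameters applies over all 16 participants or within each cohort?

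*SAP*

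**What the plan says.** SAP 7.3 codes a PK parameter that cannot be derived as NC and sets it to missing, both in summary tables and in the ANOVA. For the ANOVA it adds that "analyses will not be performed for a particular parameter if more than 50% of the data are NC". The sentence before, which opens by limiting itself to summary tables, says that "statistics will be presented for a particular hepatic function group with ≥ 3 evaluable measurements". An estimate known to be biased, for example after early vomiting, is treated separately: "this will be footnoted in summary tables and will not be included in the calculation of summary statistics or statistical analyses".

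SAP 7.2 has a similar rule for concentrations: "summary statistics will not be presented at a particular time point if more than 50% of the data are missing". It names no denominator either, but SAP 8.2 describes that table as "A summary of concentrations by hepatic function group and nominal time postdose". Protocol 9.3 leaves the matter to the SAP, which "will describe the analyses and procedures for accounting for missing, unused, and spurious data".

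The setting is small. SAP 2.1 plans dosing "in combination with the PK boosting agent ritonavir in approximately 16 participants", with 8 per cohort in its Table 1. SAP 8.1 assumes unequal variances. The example code in SAP Appendix 1 fits one residual variance per group and includes the statement "lsmeans group". SAP 6.4 lists no covariates, and SAP 4.2 has no decision rules.

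**The concern.** A percentage rule without a denominator can be read in two ways. The wording is per parameter, which points to all participants in that analysis. The neighbouring rules work by hepatic function group, which points to each cohort. If NC values cluster in one cohort, the choice decides whether the ANOVA runs.

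Read over all participants, the rule alone would let the ANOVA proceed with very few values in one cohort, even when that cohort's descriptive statistics are withheld for having fewer than 3. AUCinf is a primary endpoint and the likeliest parameter to be NC. The study is open-label and SAP 3 permits data reviews during conduct, so the reading could in principle be chosen after the counts and results are known. The results feed dosing recommendations.

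**Working it through.** **Inputs.** 8 participants per cohort (SAP 2.1, Table 1); 90% interval, log scale, unequal variances (SAP 8.1). The readable text gives no NC rate and no between-subject CV, so both are assumed over a range. The plan states no precision figure to reproduce.

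**Step 1. Where the readings part.** With k NC in Cohort 2 and none in Cohort 1, the share is k/16 or k/8:

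| k | Values left | k/16 | k/8 | Over all 16 | Per cohort |
|---|---|---|---|---|---|
| 4 | 4 v 8 | 25% | 50% | runs | runs |
| 5 | 3 v 8 | 31.25% | 62.5% | runs | withheld |
| 6 | 2 v 8 | 37.5% | 75% | runs | withheld |

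There are 9 × 9 = 81 possible splits of NC counts. The ANOVA runs in 45 on the overall reading (total at most 8) and in 25 on the per-cohort reading (at most 4 in each). The readings differ in 20. Of these, 8 leave 3 values in the smaller cohort, 6 leave 2, and 6 leave 1 or 0. These are counts of splits, not probabilities.

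**Step 2. How likely.** Assume independent NC with probability p in Cohort 2 and none in Cohort 1. Then P(k ≥ m) = Σ C(8,k) p^k (1−p)^(8−k), summed from k = m to 8:

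| p | k ≥ 5 (readings differ) | k ≥ 6 (2 or fewer left) |
|---|---|---|
| 10% | 0.04% | 0.002% |
| 20% | 1.0% | 0.1% |
| 30% | 5.8% | 1.1% |
| 40% | 17.4% | 5.0% |
| 50% | 36.3% | 14.5% |

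**Step 3. What happens to the interval.** Assume log-normal data with log SD σ = √ln(1 + CV²), equal CV in both cohorts, and a Welch-Satterthwaite 90% interval standing in for the Kenward-Roger interval of the example code. With 200,000 simulated trials per cell:

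| Values | Coverage, CV 20% to 60% | Median interval factor, CV 40% |
|---|---|---|
| 8 v 8 | 90.2% to 90.4% | 1.40 |
| 4 v 8 | 90.0% | – |
| 3 v 8 | 89.2% to 89.3% | 1.63 |
| 2 v 8 | 86.1% | 1.89 |

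The factor is the amount by which the estimated ratio is multiplied and divided to give the limits. With unequal CVs (Test 60%, Reference 30%), coverage is 88.4% at 3 v 8 and 84.3% at 2 v 8; with the CVs reversed it is 90.5% and 89.3%.

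**Step 4. One or no value.** A separate cohort variance cannot be estimated from one value, and with none there is no contrast. The unequal-variance comparison of SAP 8.1 then cannot be formed, whatever the 50% rule allows.

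**Step 5. Does 7.3 contradict itself?** At 2 v 8 on the overall reading, Cohort 2's descriptive statistics would be withheld while the model runs. With no covariates, the exponentiated Cohort 2 least-squares mean equals the geometric mean of those 2 values. But the minimum of 3 governs descriptive tables, and the model is a different output. SAP 8.2 commits to the ratio and its interval. The Appendix 1 code is labelled an example and sends the least-squares means to a dataset; no readable text says they will be tabulated by cohort. SAP 8.2 also plans box plots overlaid with geometric means and sets no minimum for them. The rules differ in scope but do not conflict.

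**The case for a change.** The best case for a change is that the repair is cheap and the rule is weak as written. Eight NC in Cohort 2 and none in Cohort 1 is exactly 50% of 16, so the overall reading does not itself bar an ANOVA with no Test data. Nor does the per-cohort reading close every gap, because known-biased values leave the ANOVA without being coded NC. Four NC (4/8 = 50%, allowed) plus 2 known-biased leaves 2 values, unless the biased values also leave the denominator (4/6 = 66.7%, withheld). A minimum of 3 evaluable values per cohort would cover both cases.

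The omission stands, and so do these examples. Their practical force does not. With no Test data there is nothing to compare, and no analyst needs a rule to see it. Four NC plus 2 known-biased combines two separate problems within eight people. Cmax and AUClast should rarely be NC: participants are confined to Day 3, and the Schedule of Activities lists 13 PK samples to 48 hours (the Synopsis mentions 24 hours).

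The worry about late choice would also survive the edit. AUCinf is analysed only when the data allow, and the readable text does not define that condition (the parameter tables did not survive extraction). A sparse AUCinf can therefore be withheld under either reading. A minimum count would only stop an ANOVA on too few values, and it would still not tell the team which denominator was meant.

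**Conclusion.** No change follows. This is an unwritten detail that analysts would fill sensibly. The plain wording points to all values of the parameter entering the ANOVA, and a sparse AUCinf can already be set aside.

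Where the readings first separate, at 3 v 8, coverage is about 89% against a nominal 90%. The drop to about 86% at 2 v 8 needs 6 of 8 NC in one cohort, and the interval is then visibly wide: a factor of 1.89 against 1.40 at CV 40%. Below 2 values the planned comparison cannot be formed. The study tests no hypothesis (Protocol 9.1) and has no decision rule, and AUClast and Cmax still carry the comparison. No effect on the study's conclusions has been shown.

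The coverage figures rest on assumed log-normal data with equal CVs of 20% to 60%, and the probabilities on assumed independent NC. A cohort NC rate of 40% or more would make the split less rare, but nothing in the documents suggests such a rate.

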8. STATISTICAL METHODOLOGY AND STATISTICAL ANALYSES

8.1. Statistical Methods

The effect of the hepatic impairment on PK parameters will be assessed by constructing 90% confidence intervals around the estimated difference between each of the Test (impaired groups) and the Reference (normal hepatic function group) using a one-way ANOVA model based on natural log transformed data and assuming unequal variances.

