#### **4.2. Scientific Rationale for Study Design**

This study is a Phase 1, non-randomized, open-label study of PF-07321332 in participants with moderate hepatic impairment and participants with normal hepatic function, matched for age, body weight and, to the extent possible, for gender composition. Details on age and body weight matching criteria are specified in [Section 5.1](#).

PF-07321332 alone is primarily eliminated through a CYP450 mediated oxidation with CYP3A4 as the major contributor ( $f_m = 0.99$ ). However, in the presence of the CYP3A4 inhibitor ritonavir, preliminary data suggests renal excretion may play a significant role in PF-07321332 excretion. In FIH study, approximately 64.6% to 32.5% of the administered dose was excreted unchanged in urine and remaining drug may get eliminated via metabolism. Preliminary PBPK modeling suggests  $< 2 \times$  increase in AUC in mild hepatic impaired participants (Child-Pugh A) and  $< 3 \times$  increase in moderate (Child-Pugh B) hepatic impaired participants. Therefore, the PK will only be evaluated in moderately hepatic impaired participants. Ritonavir has not been studied in severe hepatic impaired patients and currently prohibited to be used in those population. Therefore, this study does not plan to evaluate PK in severely hepatically impaired participants.

A single dose of PF-07321332 was selected and is considered appropriate as available data do not indicate PF-07321332 PK are time-dependent, and hence, single dose data are considered predictive of steady state. As ritonavir is not eliminated renally, multiple doses of 100 mg ritonavir will be administered at -12, 0, 12, and 24 hours relative to PF-07321332 dosing to ensure adequate PK boosting effect over the duration of PF-07321332 exposure.

PF-07321332 is not extensively bound to human plasma proteins, with  $f_u$  of 0.31 observed in the in vitro protein binding study. Thus, no additional blood samples will be collected in this study for ex vivo protein binding analysis.

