#### **Medical Conditions:**

1. Evidence or history of clinically significant hematological, renal, endocrine, pulmonary, gastrointestinal, cardiovascular, hepatic, psychiatric, neurological, or allergic disease (including drug allergies, but excluding untreated, asymptomatic, seasonal allergies at the time of dosing).
2. Any condition possibly affecting drug absorption (eg, prior bariatric surgery, gastrectomy, ileal resection).

**NOTE:** Participants who have undergone cholecystectomy and/or appendectomy are eligible for this study so long as the surgery occurred more than 6 months prior to Screening.

3. At screening, participants with a positive result for HIV antibodies.
4. **[For Cohort 1 only]** Participants with chronic liver disease including history of hepatitis, hepatitis B, or hepatitis C or evidence of active disease, at screening.  
**NOTE:** Participants with a previously positive hepatitis B surface antibody result due to vaccination are deemed eligible.

5. **[For Cohort 2 only]**
  - Hepatic carcinoma **or** hepatorenal syndrome **or** limited predicted life expectancy (defined as less than 1 year).
  - A diagnosis of hepatic dysfunction secondary to any acute ongoing hepatocellular process that is documented by medical history, physical examination, liver biopsy, hepatic ultrasound, computerized tomography scan, or MRI.
  - Signs of clinically active Grade 3 or Grade 4 hepatic encephalopathy (ie, > Grade 2 Portal Systemic Encephalopathy score; refer to [Appendix 9](#)).
  - Severe ascites and/or pleural effusion.
  - History of kidney, liver, or heart transplantation.

6. Other medical or psychiatric condition including recent (within the past year) or active suicidal ideation/behavior or laboratory abnormality or other conditions or situations related to COVID-19 pandemic (eg, Contact with positive case, residence, or travel to an area with high incidence) that may increase the risk of study participation or, in the investigator's judgment, make the participant inappropriate for the study.

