**[For Cohort 2 only]**

- Screening seated BP  $\geq 180$  mm Hg and/or  $\geq 100$  mm Hg (diastolic) following at least 5 minutes of rest.

**NOTE:** If SBP is  $\geq 140$  mm Hg (for Cohort 1) **or**  $\geq 180$  mm Hg (for Cohort 2) or if DBP  $\geq 90$  mm Hg (for Cohort 1) or  $\geq 100$  mm Hg (for Cohort 2), the BP should be repeated 2 more times and the average of the 3 BP values should be used to determine the participant's eligibility.

- For participants with SBP  $\geq 160$  (and  $<180$ ) mm Hg **or** DBP  $\geq 95$  (and  $<100$ ) mm Hg, the period between Screening and Day -1 must be used to refine the doses of the agents used for management of BP with the aim to have stable BP by Day -1. Participants must have measurement on Day 1 of SBP  $\leq 160$  mm Hg **and** DBP  $<95$  mm Hg.

16. Screening standard 12-lead ECG that demonstrates:

- Clinically relevant abnormalities requiring treatment (eg, acute myocardial infarction, serious tachy- or brady-arrhythmias) or indicating serious underlying heart disease (eg, prolonged PR interval, cardiomyopathy, underlying structural heart disease, Wolff Parkinson-White syndrome);

**[For Cohort 1 only]** Screening supine 12-lead ECG demonstrating QTcF interval  $>450$  msec or a QRS interval  $>120$  msec;

**[For Cohort 2 only]** Screening supine 12-lead ECG demonstrating a QTcF interval  $>470$  msec or a QRS interval  $>120$  msec;

**NOTE:** If QTcF exceeds 450 msec (for Cohort 1) or 480 msec (for Cohort 2), **or** QRS exceeds 120 msec, the ECG should be repeated 2 more times and the average of the 3 QTcF or QRS values should be used to determine eligibility.

17. Participants with **ANY** of the following abnormalities in clinical laboratory tests at screening, as assessed by the study -specific laboratory and confirmed by a single repeat test, if deemed necessary:

- eGFR <60 mL/min/1.73m^2 based on the CKD-EPI equation, with single repeat allowed.
- **[For Cohort 1 only]**
  - AST **or** ALT level  $\geq$  ULN;
  - Albumin > ULN;
  - Prothrombin time > ULN;
  - Total bilirubin level  $\geq 1.5 \times$  ULN;

**NOTE:** Participants with a history of Gilbert syndrome (and hence elevated total bilirubin) are eligible provided direct bilirubin level is  $\leq$  ULN;

- **[For Cohort 2 only]** ALT **or** AST  $>5 \times$  ULN

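### Should the SAP have planned an eGFR-adjusted AUC ratio because boosted PF-07321332 may be cleared substantially by the kidney?

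*SAP*

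**What the plan says.** SAP 8.1 compares the log-transformed PK parameters of the two cohorts "using a one-way ANOVA model based on natural log transformed data and assuming unequal variances". Under the heading "6.4. Covariates" the SAP states that there are none. The code in Appendix 1 agrees: "model l&var = group / S covb alpha=0.1 CL DDFM=KR" has group as its only fixed effect.

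Protocol 4.2 notes that, with ritonavir, "preliminary data suggests renal excretion may play a significant role in PF-07321332 excretion", and that in the first-in-human study "approximately 64.6% to 32.5% of the administered dose was excreted unchanged in urine".

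According to SAP 2.1, Cohort 1 is to "match the average demographics (at a minimum, age and weight; gender and race as much as practically possible") of Cohort 2. Protocol 5.1 limits each Cohort 1 participant to within 10 years of the Cohort 2 mean age. Renal function is not a matching factor, but eligibility restricts it. In both cohorts an eGFR below 60 mL/min/1.73m² is excluded, "based on the CKD-EPI equation, with single repeat allowed" (Protocol 5.2, criterion 17). Criterion 1 excludes "Evidence or history of clinically significant hematological, renal, endocrine, pulmonary" and other clinically significant disease. Criterion 5 also excludes hepatorenal syndrome and kidney transplantation in Cohort 2.

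No hypothesis is tested (Protocol 9.1, SAP 4.1), and SAP 4.2 states that no decision rules are needed.

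**The concern.** The cohorts are not randomized, and the protocol itself names a second route of elimination. If the cohorts differ in eGFR, a group-only model attributes the resulting difference in exposure to the liver. Residual plots would not show this, because the group term absorbs a cohort-level shift. The ratio is to inform dosing recommendations in hepatic impairment, so a distortion in either direction would matter. Creatinine, age, sex and race are already collected, so one pre-specified model with ln eGFR added seems to cost almost nothing.

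**Working it through.** **Inputs from the documents.** Renal share of clearance fe = 0.325 to 0.646, taking urinary recovery as that share (Protocol 4.2). Eight participants per cohort, 90% CI, log scale. Lower eGFR limit 60.

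**Assumptions.** The visible text gives no between-participant CV and no expected eGFR difference. I use CVs of 30% and 40%, and mean eGFR in Cohort 2 of 90, 80 or 70 against 100. Renal clearance is taken as proportional to eGFR.

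**Step 1: size of the distortion.** With equal non-renal clearance and eGFR ratio r, the AUC ratio produced by eGFR alone is 1/(1 − fe × (1 − r)). For example, 1/(1 − 0.646 × 0.2) = 1.148.

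The 90% CI half-width on the log scale is t(0.95, 14) × √ln(1 + CV²) × √(2/8):
- CV 30%: 1.761 × 0.2936 × 0.5 = 0.2585, a factor of 1.295.
- CV 40%: 1.761 × 0.3853 × 0.5 = 0.3393, a factor of 1.404.

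| eGFR, Cohort 2 vs 1 | AUC ratio, fe 0.325 | AUC ratio, fe 0.646 | Share of log half-width |
|---|---|---|---|
| 90 vs 100 | 1.034 | 1.069 | 10% to 26% |
| 80 vs 100 | 1.070 | 1.148 | 20% to 54% |
| 70 vs 100 | 1.108 | 1.240 | 30% to 83% |

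The distortion is inside the half-width in every case. It is also modest against the projected increase of less than 3-fold in Protocol 4.2.

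**Step 2: what adjustment costs in variance.** The adjusted log ratio is the unadjusted one minus b × Δ, where b is the estimated slope on ln eGFR and Δ is the cohort difference in mean ln eGFR. Adjustment removes a bias of about fe × Δ and adds a standard error of about SE(b) × Δ. Mean squared error therefore falls only if fe exceeds SE(b), roughly.

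Take an eGFR SD of 15 around 100, so about 0.15 on the log scale, and 14 within-cohort degrees of freedom for the spread of eGFR. Then SE(b) ≈ √ln(1 + CV²)/(0.15 × √14):
- CV 30%: 0.2936/0.561 = 0.52.
- CV 40%: 0.3853/0.561 = 0.69.

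Only fe = 0.646 with CV 30% passes (0.646 > 0.52). The other three combinations of fe and CV fail.

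**Step 3: simulation.** There were 20,000 trials per setting with 8 per cohort, eGFR SD 15 truncated at 60, no hepatic effect and eGFR known without error. The planned analysis is represented by a Welch interval, and the adjusted one by a pooled-variance ANCOVA on ln eGFR. Root mean squared error of the log ratio, unadjusted then adjusted:

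| fe, CV | 90 vs 100 | 80 vs 100 |
|---|---|---|
| 0.325, 30% | 0.152, 0.164 | 0.159, 0.187 |
| 0.325, 40% | 0.197, 0.213 | 0.202, 0.249 |
| 0.646, 40% | 0.209, 0.213 | 0.232, 0.246 |
| 0.646, 30% | 0.167, 0.163 | 0.196, 0.186 |

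The adjusted ratio has the larger error in 6 of 8 settings, as Step 2 predicts. It is farther from the truth than the planned ratio in 44% to 58% of trials. The slope has the wrong sign in 12% to 33%.

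**Step 4: error in eGFR.** With an assumed 15% log-scale error in eGFR (80 vs 100, fe 0.646, CV 30%), the adjusted ratio is still about 1.06, against 1.13 unadjusted. Since ln 1.06/ln 1.13 = 0.058/0.122 = 0.48, about half the bias remains.

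**The case for a change.** The case for the extra analysis is real. The facts it rests on are correct: renal excretion is flagged, matching leaves out renal function, and the model has no covariate. Eligibility limits the imbalance but does not remove it, since every case in Step 1 lies above the floor of 60. Under the assumed bias, adjustment also does what it promises on average. At 80 vs 100, planned 90% CI coverage is about 0.81 to 0.89 in this simulation, where truncation lifts the realised Cohort 2 mean to about 83. It falls as low as 0.784 if the means are held at 80 and 100 after truncation. The adjusted interval covers about 0.90. A covariate named in advance is also more credible than one chosen after the ratio is known.

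Three things weigh against it:
- **Precision.** Correct coverage comes from a wider interval around a noisier estimate. At 80 vs 100, with the means held, the half-width factor rises from 1.29–1.41 to 1.39–1.54. Agreement or disagreement between the two ratios would often reflect slope noise.
- **Target.** The study asks how exposure changes in people with hepatic impairment. If liver disease lowers GFR, that reduction is part of the answer. An adjusted ratio leaves it out and estimates a different quantity.
- **Model.** The gains above come from a pooled-variance ANCOVA. Adding a term to the Appendix 1 code would keep cohort-specific variances and Kenward-Roger degrees of freedom, and that model's performance has not been shown.

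Parts of the PK text in both documents are redacted. The visible text establishes only that the model has no renal covariate; it does not establish that renal function is left out of every summary.

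**Conclusion.** The concern does not hold as a fault in the plan. A cohort difference in eGFR could move the AUC ratio by 3% to 15% for 90 or 80 against 100, and by up to 24% for 70 against 100. These figures rest on assumed eGFR differences and on renal clearance being proportional to eGFR. The eligibility limits, the exclusions and matching on age (with sex and race where practical) all work against a large imbalance. SAP 8.3.5 summarizes baseline laboratory values by cohort, and creatinine is in the chemistry panel, so an imbalance would not go unseen.

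With 16 participants, adjustment exchanges a modest possible bias for added variance and usually loses on total error at the CVs assumed here. It would win with a high renal share and a low CV, so statisticians could reasonably choose either way. The planned ratio answers the stated question, and no decision rule depends on a second one. Leaving the adjusted analysis out is a matter of preference, and nothing needs to change.
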